6.3.1. Incidence of Vertebral Fracture

| | |
|---------------------|--|
| 1) Analysis set | Patients evaluated for efficacy with dates of pre- and post-treatment ^{*1} radiography Patients evaluated for vertebral fracture |
| 2) Chart plan | Table 3-1-1-1 Table 3-1-1-2 Table 3-1-1-3 Table 3-1-1-4 Table 3-1-1-5 Table 3-1-1-6 Table 3-1-2-1 Table 3-1-2-2 Table 3-1-2-3 Table 3-1-2-4 Table 3-1-2-5 Table 3-1-2-6 |
| 3) Analysis items | New vertebral fracture or worsening of prevalent fracture New vertebral fracture or worsening of prevalent fracture <non-traumatic> New vertebral fracture New vertebral fracture <non-traumatic> Worsening of prevalent fracture Worsening of prevalent fracture <non-traumatic> |
| 4) Analysis methods | For the time to the first onset of the analysis item, the point estimate of cumulative incidence, standard error, and 95% confidence interval will be calculated using the Kaplan-Meier method, and the number of relevant patients (number of patients at risk), cumulative number of patients with |

the analysis item, and cumulative number of censored patients at Month 6 (Day 180), Month 12 (Day 360), Month 18 (Day 540), Month 24 (Day 720), Month 30 (Day 900), and Month 36 (Day 1096) will be calculated. In addition, a Kaplan-Meier curve will be plotted with the cumulative incidence (%) on the vertical axis and the time (months) on the horizontal axis. The number of relevant patients (number of patients at risk) will be presented under the time (months).

The time to the first onset of the analysis item is defined as time from the start date of Benet/Actonel treatment to the earliest date of radiography with a diagnosis of the analysis item. Patients with no analysis item will be censored at the latest date of radiography with no evidence of the analysis item.^{*2}

No radiographic data collected after the end date of Benet/Actonel treatment + 90 days or after 3 consecutive months (90 days) of interruption in patients with interruption of treatment will be used for analysis.

*1 Range of assessment before and after treatment

- Before treatment: before the start of Benet/Actonel treatment defined as Days -90 to 1
- After treatment: before the end date of Benet/Actonel treatment + 90 days, and before 3 consecutive months (90 days) of interruption in patients with interruption of treatment

*2 The date of radiography with no evidence of the analysis item is defined as follows for each analysis set:

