6.3.3. Incidence of Vertebral Fracture Event at Each Time Point of Assessment

| | |
|---------------------|--|
| 1) Analysis set | Patients evaluated for vertebral fracture |
| 2) Chart plan | Table 3-3-1 Table 3-3-2 |
| 3) Analysis items | New vertebral fracture or worsening of prevalent fracture New vertebral fracture or worsening of prevalent fracture <non-traumatic> |
| 4) Analysis methods | The number of relevant patients, observed person·years, number of patients with the first onset of the analysis item, and incidence rate (number of patients with event/100 person·years) in the range of assessment at each time point of assessment (see below) will be calculated, and the ratio of incidence rate at each time point of assessment relative to Month 6 and its 95% confidence interval will be calculated. Handling of onset day of the analysis item and data for analysis will be as specified in Section 6.3.1, “Incidence of Vertebral Fracture.” |

Observed person·years: (1)+2)) ÷ 12

1): (Number of patients with radiography, no event, and no censoring in the range of assessment at each time point of assessment) \times 6

A patient with no radiography at the relevant time point of assessment, but with valid radiography at any later time point will be counted at the relevant time point of assessment.

2): Total time (months) from the start date of assessment to event or censoring in the range of assessment at each time point of assessment for patients with event or censoring

Incidence rate: (number of patients with event \div observed person-years) \times 100

Range of assessment at each time point of assessment

| Time point of assessment | Range of assessment |
|--------------------------|---------------------|
| Month 6 | Days 2 to 180 |
| Month 12 | Days 181 to 360 |
| Month 18 | Days 361 to 540 |
| Month 24 | Days 541 to 720 |
| Month 30 | Days 721 to 900 |
| Month 36 | Days 901 to 1096 |

No radiographic data collected after the end date of Benet/Actonel treatment + 90 days or after 3 consecutive months (90 days) of interruption in patients with interruption of treatment will be handled as data in the range of assessment (not used for analysis).

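### SAP Section 6.3.3 credits a flat 6 months to patients followed event-free past Day 1096, although the Month 36 range is 196 days long, so their person-time is too small

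*SAP*

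**What the plan says.** Section 6.3.3 of SAP 5.1 tabulates a vertebral fracture rate per 100 person-years in six consecutive ranges, and the ratio of each rate to the Month 6 rate with a 95% confidence interval. Observed person-years are the sum of two parts, in months, divided by 12.

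- Part 1) is a count times 6. The count is the "Number of patients with radiography, no event, and no censoring in the range of assessment at each time point of assessment". A patient without a film in a range is also included if there is a later one: such a patient "with valid radiography at any later time point will be counted at the relevant time point of assessment".
- Part 2) covers patients who have an event or are censored in the range. It is the "Total time (months) from the start date of assessment to event or censoring in the range of assessment at each time point of assessment".

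Data handling follows Section 6.3.1, which sets the censoring date: "Patients with no analysis item will be censored at the latest date of radiography with no evidence of the analysis item". Films are usable until 90 days after the end date of treatment, and Section 5.5 puts that end date 30 days after the last dose taken.

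Month 6 covers Days 2 to 180. Month 12 covers "Days 181 to 360", and Months 18, 24 and 30 have the same length. Month 36 covers "Days 901 to 1096".

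**The concern.** One constant is used for ranges of different length. It suits every range except the last, which is 16 days longer than the 180 days that 6 months represents. In that range the two parts of the denominator disagree: a patient censored on Day 1096 receives about 6.5 months under part 2), while a patient followed beyond Day 1096 receives only 6 under part 1). Longer follow-up should not earn less person-time.

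The purpose of the table is to show whether the fracture rate changes during treatment, through ratios to Month 6. A denominator that is short in one range only distorts that comparison, and the confidence interval does not reflect it.

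**Working it through.** **Inputs.** The range limits, the factor of 6 and the division by 12 come from SAP 5.1 Section 6.3.3. The censoring date and film cut-off come from Section 6.3.1. Section 6.3.3 states no days-per-month conversion. Section 5.5 uses 30, but for treatment duration only, so 30 is an assumption here and 365.25/12 = 30.44 is the alternative.

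**Step 1: does the 6-month credit reproduce?** Length = last day − first day + 1.

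| Range | Days | Months at 30 | Length ÷ credit at 30 | Length ÷ credit at 30.44 |
|---|---|---|---|---|
| Month 6 | 180 − 2 + 1 = 179 | 5.97 | 0.994 | 0.980 |
| Months 12, 18, 24, 30 | 180 each | 6.00 | 1.000 | 0.986 |
| Month 36 | 1096 − 901 + 1 = 196 | 6.53 | 1.089 | 1.073 |

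At 30 days per month the credit is exact for Months 12 to 30 and 0.6% off for Month 6. It fails for Month 36.

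**Step 2: who is affected?** An event-free patient whose last film falls on Days 901 to 1096 is censored in the range and gets actual time, without error. Only a patient still under valid radiographic follow-up after Day 1096 gets the flat 6. A patient censored on Day 1096 gets 195/30 = 6.50 or 196/30 = 6.53 months, depending on whether the first day is counted.

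**Step 3: can films after Day 1096 occur?** Yes. The protocol (Section 9.2.5) schedules a film at 36 months. Every 36-month span starting between May 2013 and October 2014 contains 29 February 2016, so the anniversary is 3 × 365 + 1 = 1096 days after Day 1, that is Day 1097. If the last dose is near Day 1066 (36th monthly dose, 1 + 35 × 30.44), films are usable to about Day 1066 + 30 + 90 = 1186.

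**Step 4: size of the denominator error alone.** Let s be the share of patients with a valid film after Day 1096, and c the average days into the range at which the others are censored. With no events:

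overstatement of the rate = [s × 196/30 + (1 − s) × c/30] ÷ [s × 6 + (1 − s) × c/30] − 1

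| s | c = 180 | c = 90 |
|---|---|---|
| 100% | 8.9% | 8.9% |
| 75% | 6.7% | 7.6% |
| 50% | 4.4% | 5.9% |
| 25% | 2.2% | 3.6% |
| 10% | 0.9% | 1.6% |
| 0% | 0% | 0% |

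The values of s and c are assumptions; the documents give neither. With 10 events among 200 patients, also assumed, the 50% row becomes 4.2% and 5.7%. The ceiling for the rate is 196/180 − 1 = 8.9%, or 7.3% with 30.44-day months.

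**Step 5: the ratio to Month 6.** Month 6 is credited 6 months for 179 days, so its own rate is slightly understated. If both ranges consist wholly of flat credit, the ratio error is 196/179 − 1 = 9.5%, whatever the month length. If Month 6 is taken as 180 days, it is 8.9%.

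**Step 6: the numerator at the same boundary.** A fracture first seen on a film after Day 1096 lies in no range and is not counted. At the ceiling, losing 1 of 10 events gives 0.9 × 1.089 = 0.98, so the Month 36 rate is then slightly too low. Losing 2 of 10 gives 0.8 × 1.089 = 0.87.

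**The case against.** The strongest reply is that the error may be empty. Section 6.3.3 defines no time point after Month 36, so a film after Day 1096 might not count as a later film at all. If follow-up in this table were cut at Day 1096, the patients concerned would be censored in the range, receive actual time, and the error would vanish. But neither Section 6.3.1 nor 6.3.3 censors at Day 1096. A patient with one film inside the range and another event-free film after it meets part 1) on a plain reading. A patient whose only late film falls after Day 1096 gets 6 months if that film counts. If it does not, the patient fits neither part and gets nothing, which makes the shortfall larger.

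The reply does limit what may be concluded. A reader might infer that all event-free patients in the Month 36 range are under-credited; part 2) excludes that. A reader might also infer that the fracture rate late in treatment will look higher than it is. The documents do not support this, because the situation that maximises the denominator error, with nearly all last films after Day 1096, is also the one in which fractures found on the scheduled 36-month film drop out of the numerator.

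The objection on materiality stands as well. The main analysis of vertebral fracture is the Kaplan-Meier cumulative incidence in Section 6.3.1, which uses no person-time credit. Section 6.3.3 is a supplementary table with no significance test or decision attached. With an assumed 10 events in each of two ranges, the 95% limits of a rate ratio lie at a factor of about exp(1.96 × √(1/10 + 1/10)) = 2.4 either side, far wider than an error of at most 9.5%.

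**Conclusion.** The rule is wrong as written; its materiality is minor. For patients followed event-free past Day 1096, Month 36 person-time is credited at 180/196 = 91.8% of its length on a 30-day month. The resulting inflation, within the bounds in steps 4 and 5, depends on the share of these patients, which the plan does not allow one to predict. It also rests on treating films after Day 1096 as valid, which the 90-day film rule supports but Section 6.3.3 does not state.

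The bound describes the denominator error alone. The net error of the Month 36 rate may have either sign until the handling of fractures first seen after Day 1096 is settled.

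**What to change.** In Section 6.3.3, calculate part 1) from the actual days at risk in each range, as part 2) already does. Alternatively, replace the constant by each range's own length, which for Month 36 is 196/30 = 6.53 months. State one days-per-month conversion for the section and use it in both parts. State one rule for films after Day 1096 and apply it to both numerator and denominator: either follow-up in this table ends on Day 1096 and later films add neither events nor time beyond it, or the last range is extended and its person-time extended with it.

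The cost is a few lines of SAP text and a small change to the program. No new data are needed and no procedure at the sites changes. Changing the constant alone would leave the month length and the numerator question open, so the three statements should be made together.

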6.3.4. Percent Changes in Bone Turnover Markers

- 1) Analysis set Patients evaluated for efficacy with pre- and post-treatment values of bone turnover markers
- 2) Chart plan Table 3-4
- 3) Analysis items Bone turnover markers
- 4) Analysis methods For each bone turnover marker, summary statistics at each time point of assessment will be calculated for observed value and percent change. In addition, the 95% confidence interval for percent change will be calculated, and p-value will be calculated as specified in Section 3.3. 4), “Rules of statistical testing.”

6.3.5. Percent Change in Bone Mineral Density

- | | |
|---------------------|---|
| 1) Analysis set | Patients evaluated for efficacy with pre- and post-treatment values of bone mineral density |
| 2) Chart plan | Table 3-5 |
| 3) Analysis item | Bone mineral density |
| 4) Analysis methods | For each bone mineral density, summary statistics at each time point of assessment will be calculated for observed value and percent change. In addition, the 95% confidence interval for percent change will be calculated, and p-value will be calculated as specified in Section 3.3. 4), “Rules of statistical testing.” If a check is made to lumbar spines 2) to 4) in the “Location of vertebral fracture” in the CRF after the start of Benet/Actonel treatment, no data on lumbar spine (DXA) bone mineral density dated the relevant date or later will be employed. |

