4.0 Surveillance Population

Osteoporotic patients will be included in the surveillance. The selection criteria listed below should also be met, and the precautions concerning indications in the package insert should be referred to.

Selection criteria

Patients meeting all of the following criteria will be included in the surveillance:

- 1) A patient with evidence of 1 to 4 fractures from the fourth thoracic vertebra to the fourth lumbar vertebra (T₄ to L₄) provided by thoracic and lumbar spinal radiography performed before the start of the surveillance (within 3 months before the start of prescription of Benet)
- 2) A patient aged 50 years or older (menopausal if female)
- 3) An outpatient who can walk

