9.2.5 Assessment of Vertebral Fracture

1) Surveillance items

Vertebral fracture before the start of Benet treatment (baseline) will be confirmed, and the date of radiography, radiographic location, and location of vertebral fracture will be entered into the CRF. Then, the presence or absence and location of new vertebral fracture, presence or absence of worsening of prevalent vertebral fracture, and presence or absence of apparent trauma during treatment and at the end of the observation period (or discontinuation of treatment) relative to baseline will be entered into the CRF.

2) Time points of surveillance

At the start of Benet treatment, 12, 24, and 36 months after the start of treatment (or discontinuation of treatment), and when vertebral fracture is suspected during the observation period

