4.5. Patients Evaluated for Vertebral Fracture

All patients evaluated for efficacy, excluding those who meet any of the following criteria:

1) No evidence of 1 to 4 fractures from the fourth thoracic vertebra to the fourth lumbar vertebra provided by thoracic and lumbar spinal radiography performed before the start of the surveillance^{*}

* The permissible range before the start of the surveillance is Days -90 to 1.

2) Not 50 years or older

3) Not an outpatient who can walk

4) No known date of pre- or post-treatment^{*} radiography for assessment of vertebral fracture

* For the permissible range before or after treatment, refer to *1 in Section 6.3.1.

5. Handling of Data

Handling of data for analysis is described below. Details of processing will be specified in separately prepared analysis data set specifications.

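### As documented, the lumbar DXA exclusion in SAP 6.3.5 does not cover on-treatment worsening of a prevalent L2–L4 fracture

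*SAP*

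**What the plan says.** **The exclusion rule.** SAP 6.3.5 (version 5.1) begins "If a check is made to lumbar spines 2) to 4) in the" CRF field for fracture location. It applies to ticks made "in the CRF after the start of Benet/Actonel treatment, no data on lumbar spine (DXA) bone mineral density dated the relevant date or later" and stops those values being used. The text says neither new nor worsened.

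**What is recorded.** Protocol 9.2.5 says that at baseline "the date of radiography, radiographic location, and location of vertebral fracture will be entered into the CRF". After baseline the items are "the presence or absence and location of new vertebral fracture, presence or absence of worsening of prevalent vertebral fracture", plus apparent trauma. Level is attached to the baseline and new fractures. Worsening gets a yes or no.

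**Who is enrolled.** Protocol 4.0, first criterion: "A patient with evidence of 1 to 4 fractures from the fourth thoracic vertebra to the fourth lumbar vertebra".

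**Who is analysed for bone density.** SAP 6.3.5 uses "Patients evaluated for efficacy with pre- and post-treatment values of bone mineral density". The exclusion for "No evidence of 1 to 4 fractures from the fourth thoracic vertebra to the fourth lumbar vertebra" stands in SAP 4.5 (the vertebral fracture set) and not in SAP 4.4 (the efficacy set).

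**Status of worsening.** SAP 6.3.1 analyses "worsening of prevalent fracture" as an event of its own, alone and combined with new fracture.

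**The concern.** By dropping later lumbar DXA after an on-treatment L2–L4 fracture, the SAP accepts that such a fracture spoils the measurement. The same reasoning applies when a vertebra already fractured at baseline collapses further. Areal density is mineral content divided by projected area, so a loss of height can raise the reading without any gain in bone.

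The population is selected for prevalent vertebral fractures, so this situation is foreseeable. Percent change in bone mineral density is named in the objective (Protocol 2.0). It is tested within patients with no control group (SAP 3.3, 6.3.5), so no comparator cancels an artefact that runs in one direction. One radiographic event could then count as a fracture in 6.3.1 and as a lumbar density gain in 6.3.5.

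**Working it through.** **Plan figures.** The documents give no expected bone density change, SD, worsening rate or degree of collapse, so there is no figure on this point to reproduce. The one design figure, 250 / (1 − 0.5) = 500 patients (Protocol 3.2), reproduces and is not affected.

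**Does a worsened L2–L4 fracture trigger the rule?**

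| Event | Level recorded (Protocol 9.2.5) | After treatment start | Triggers SAP 6.3.5 |
|---|---|---|---|
| Prevalent L2–L4 fracture, stable | yes, at baseline | no | no |
| New L2–L4 fracture | yes | yes | yes |
| Prevalent L2–L4 fracture, worsened | no, yes/no only | yes | no, as documented |

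The first row is harmless for percent change, because a stable deformity affects baseline and follow-up alike. The third row is the gap. No other SAP rule removes these values, and no sensitivity analysis is planned.

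**How many could be exposed?** T4–L4 is 13 levels, of which L2–L4 are 3. If all levels are equally likely (assumption), the probability of at least one L2–L4 fracture among k is 1 − C(10,k)/C(13,k):

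- k = 1: 1 − 10/13 = 23%
- k = 2: 1 − 45/78 = 42%
- k = 3: 1 − 120/286 = 58%
- k = 4: 1 − 210/715 = 71%

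These are shares with a baseline L2–L4 fracture, not shares affected.

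**Artefact in one patient.** Suppose one of three equal-area vertebrae loses a fraction h of its height, and mineral falls by a fraction f of the proportional loss. Measured density changes by (1 − f·h/3)/(1 − h/3) − 1.

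| | h = 10% | h = 20% | h = 40% |
|---|---|---|---|
| f = 0 (mineral unchanged) | +3.4% | +7.1% | +15.4% |
| f = 0.5 | +1.7% | +3.6% | +7.7% |
| f = 1 (mineral falls with area) | 0 | 0 | 0 |

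For h = 20%, f = 0: 1/(1 − 0.0667) = 3/2.8 = 1.071.

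**Shift in the mean** (h = 20%, f = 0), with a share q of lumbar DXA patients affected (assumption): q × 7.14 points.

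- q = 1%: 0.07
- q = 2%: 0.14
- q = 5%: 0.36
- q = 10%: 0.71

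For scale, an assumed SD of 4–6% and n of 100–250 give a standard error between 4/√250 = 0.25 and 6/√100 = 0.60 points. On the equal-levels assumption, q = 10% would need between 0.10/0.706 = 14% (four fractures) and 0.10/0.231 = 43% (one fracture) of patients with a baseline L2–L4 fracture to worsen at that level. For q = 1% the range is 1.4% to 4.3%. The upper end of q is therefore demanding.

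**p-value.** The statistic depends on mean/SD, and a few raised values also widen the SD. Assume a true mean of +5%, q = 5%, and 7.14 points added to each affected value. The mean becomes 5.36 and the variance rises by 0.05 × 0.95 × 7.14² = 2.42.

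- SD 3%: 5/3 = 1.67 becomes 5.36/√11.42 = 5.36/3.38 = 1.59, so p rises.
- SD 4%: 1.25 becomes 5.36/√18.42 = 1.25, essentially unchanged.
- SD 6%: 0.83 becomes 5.36/√38.42 = 0.86, so p falls.

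**The case against.** The strongest reply is that the rule is silent on worsening but does not exclude it. SAP 6.3.5 refers to any L2–L4 tick after treatment start, and the CRF is not in the documents, so a site might tick the level of a worsened vertebra. Protocol 9.3 also sends worsening to the adverse event column, where the term may name the level, and SAP section 5 leaves processing details to separate specifications.

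This stands in part. A reader might infer that a worsened fracture can never trigger the rule. The documents do not support that; they show only that the recorded items supply no level for it. The uncertainty does not rescue the rule, however. If the post-baseline field lists every fracture present, stable L2–L4 fractures would trigger exclusion as well. The limit to ticks after treatment start is absent from SAP 4.0 (6.3.6) and present in SAP 4.1 (6.3.6), so keeping patients with a baseline L2–L4 fracture appears deliberate. Either way, 6.3.5 has to say what counts.

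Three further points stand:

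- **Exposure.** Because all eligible patients have prevalent fractures, a reader might take them all as affected. The artefact needs a fracture at L2–L4, further collapse there on treatment, and lumbar DXA both at baseline and after the collapse. The bone density set is also not restricted to patients who meet the fracture criterion.
- **Size.** Unchanged mineral is the largest case considered. At 1–2% affected, the shift is below the assumed standard error.
- **Scope.** Protocol 9.2.4.2 also lists proximal femur, radius, calcaneus and metacarpal, which vertebral collapse does not touch.

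**Conclusion.** The gap holds. Followed as written, with data collected as Protocol 9.2.5 describes, the rule keeps lumbar DXA values that the SAP's own logic treats as unusable.

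The artefact is upward or zero. In an affected patient it is about +7% for 20% height loss in one of three equal vertebrae with mineral unchanged, and nil if mineral falls in proportion to area. With 1–10% of lumbar DXA patients affected, the mean percent change is inflated by about 0.07–0.7 points. Height loss, mineral change and affected share are all assumptions.

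Two stronger conclusions are tempting and not supported. A reader might infer that the p-value is pushed down in favour of the drug; the example shows it can move either way, because the SD grows too. A reader might also infer that the fracture result is compromised; the primary endpoint is untouched, and the point is confined to the lumbar site of a secondary endpoint.

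**What to change.** In SAP 6.3.5:

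1. State whether worsening counts. Where the baseline fracture location includes L2–L4 and worsening of a prevalent fracture is recorded after treatment start, do not use lumbar DXA dated on or after the radiograph that showed it, unless the CRF or the adverse event entry shows that the worsened level is outside L2–L4.
2. Add one supporting lumbar table in patients with no L2–L4 fracture at baseline.

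The data are already collected: baseline level and presence of worsening (Protocol 9.2.5), and the date of the diagnosing radiograph (used in SAP 6.3.1).

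The cost is a change of wording and one table. Some valid lumbar DXA values will be lost when the worsened level is unknown and in fact lies outside L2–L4. Like the existing rule, this one acts from the radiograph date, so a DXA taken between the collapse and its detection stays in. The supporting table is free of the worsening artefact altogether.
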